8. RISKS AND BENEFITS

List all potential physical, psychological, social, financial or legal risks to subjects (risks listed here should be included on the consent form).

Minimal risks to the subjects are expected. The risks of the physical therapy interventions might include muscular strain/soreness. A small risk of a fall (and concurrent injury) during functional performance testing or functional hip strengthening is present. As with any physical activity, there is the possibility that the participant's typical symptoms in the low back and/or hip might increase, although unlikely. There is also the potential for new musculoskeletal pain to occur secondary to physical activity. With increased or new symptoms, the treating therapist will modify the intervention. Study participants will be free to withdraw from participating in the study at any time if they are uncomfortable with any of the procedures. Although no other risks or changes in the existing minimal risks are anticipated, participants will be informed if any new information arises regarding risks of participation that may affect their decision to continue in the study.

In your opinion, are risks listed above minimal* or more than minimal? If more than minimal, please justify why risks are reasonable in relation to anticipated direct or future benefits.

We consider these risks to be minimal given that proposed functional performance tasks are similar to those performed in daily activities and commonly used during physical therapy evaluations, and that the interventions included in this clinical trial are those typically prescribed by physical therapists to reduce musculoskeletal complaints.

*(*Minimal risk means the probability and magnitude of harm or discomfort anticipated in the research are not greater than those ordinarily encountered in daily life or during the performance of routine physical or psychological examinations or tests)*

What steps will be taken to minimize risks?

A licensed physical therapist will be present to appropriately assist the participant for all functional performance testing and functional hip strengthening, where there may be an increased risk of falling. Physical therapists will monitor low back and hip pain (and document any new pain), which will allow for treatment modification, as needed. Overall, the supervision of a licensed physical therapist should minimize potential risk, especially since the testing and treatment offered within the context of this study is used on a daily basis by physical therapists in the clinical setting.

Describe any potential direct benefits to participants.

The benefits of this study include free evaluations by a licensed physical therapist that will provide individuals with detailed information concerning their low back and hip pain. Participants will receive 8 weeks of physical therapy services with no out-of-pocket expenses.

Describe any potential future benefits to this class of participants, others, or society.

The potential benefits of this research include (a) improvement of quality-of-life of community-dwelling older adults with chronic low back pain through improved pain management, physical, and/or psychosocial function; (b) development of an alternative non-pharmacologic treatment for older adults with chronic low back pain, and thus protection of future individuals from exposure to potentially toxic medications; (c) a possible decrease in pain and thus, an increase in independence among older adults with chronic LBP, and (d) generation of data for future studies that may lead to decreased health care utilization costs.

If there is a Data Monitoring Committee (DMC) in place for this project, please describe when and how often it meets.

The Principal Investigator ([name]), along with the site PI's, will be responsible for ensuring participants' safety on a daily basis. The *Data and Safety Monitoring Board (DSMB)* will act in an advisory capacity to the NIA Director to monitor participant safety, evaluate the progress of the study, to review procedures for maintaining the confidentiality of data, the quality of data collection, management, and analyses. The DSMB will have a Safety Officer (SO); the SO will not be involved in the study in any other way. The DSMB reviewed and approved the study protocol on 8/19/2019 (i.e. prior to initiation of enrollment). The PI will be informed of serious adverse events as soon as they occur and will notify the NIA and DSMB within 24 hours of notification. The *DSMB* will meet twice annually by teleconference call to review study progress, data quality, and participants' safety.

9. COMPENSATION

Will participants be compensated for participation?

Yes

If so, please include details.

Compensation will be provided to all participants for their time and participation in the study. Payment will be in the following increments: \$75 after completion of the 8 week re-evaluation and \$50 after study completion, i.e. at 6 months. If a potential participant is found ineligible after the on-site screening process, they will receive pro-rated compensation in the amount of \$20. Compensation will be provided via mail 3-4 weeks after each of these time points.

10. DATA

Will subjects be anonymous to the researcher? No

If subjects are identifiable, will their identities be kept confidential? (If yes, please specify how)

Yes, but their identity will be kept confidential. Participants will be assigned subject identification (ID) numbers. A web-based data management system, developed by the University of Pittsburgh Physical Therapy Data Center (PTDC), which is secure, encrypted, and password-protected, will be used for data entry and management. Electronic versions of all data collection instruments have

been created, so as to create a paperless data entry system. All data entry will be completed on tablets and/or computers. Data will be stored on University of Pittsburgh servers maintained by the Network Operations Center and will be accessible by PTDC staff only. Back-up copies of analysis files and programs used to prepare scientific publications will be maintained and archived indefinitely.

There may be plans to use identifiable data for other research studies outside the scope of this study, as such to recruit participants interested in participating in a separate study, therefore we will ask them on the informed consent. If the participant verbally consents to be contacted in the future for another study or purpose, their name, age, and contact information will be kept in a separate password protected folder under an encrypted UD server.

How will data be stored and kept secure (specify data storage plans for both paper and electronic files. For guidance see <http://www.udel.edu/research/preparing/dastorage.html>)

Original informed consents will be stored at the clinical site in a locked file cabinet that is accessible only to research personnel. Paper charts for treating therapists that include comorbidity and medication data will be securely stored in a locked file cabinet that is only accessible to research personnel. Electronic data will be stored in the electronic system and only research study personnel will be issued passwords. Recontact information for future studies will be stored in a separate password protected folder on an encrypted UD server.

Each study participant will be assigned a Study Identification Number (SID). The participant names and contact information will be stored in a separate form of the electronic data collection system that is not in the same tables as the research data. Name and contact information will be available to the local site of the participant and to the systems analyst and data manager of the Data Coordinating Center at the University of Pittsburgh. No other persons will have access to names and contact information. Only the research team will be issued passwords to access data.

How long will data be stored?

Data will be securely stored indefinitely for future/additional research purposes. All data collected will be held in locked files in areas accessible only to research personnel. In the informed consent, participants will have the option to choose 'yes or no' in regards to being contacted for future studies. If the participant chooses to be re-contacted, then we will keep their name, age, and contact information for future use to communicate with the participant.

Will data be destroyed? YES NO (if yes, please specify how the data will be destroyed)

Will the data be shared with anyone outside of the research team? YES NO (if yes, please list the person(s), organization(s) and/or institution(s) and specify plans for secure data transfer)

Research records may be viewed by the University of Delaware Institutional Review Board, which is a committee formally designated to approve, monitor, and review biomedical and behavioral research involving humans and by the National Institutes of Health, the government agency that is sponsoring this research.

Additionally, the following individuals are investigators on this project at the other sites, and will have access to the data:

[name] – University of Pittsburgh Physical Therapy Clinical and Translational Research Center (PT-CTRC)

[name] – University of Pittsburgh Physical Therapy Clinical and Translational Research Center (PT-CTRC)

[name] – University of Pittsburgh School of Medicine

[name] – Duke Clinical Research Institute

[name] – Duke Clinical Research Institute

How will data be analyzed and reported?

Statistical Analysis: [name] will supervise the data analyses for this proposal along with [name] and all analyses will be performed using SAS software, version 9.4 (SAS Institute, Inc., Cary, NC). The primary analyses will be done using intention-to-treat methods. We will compare the two groups on baseline characteristics to assess the adequacy of the randomization. Baseline characteristics include analgesic use, age, number of comorbidities, body mass index, gender, and race/ethnicity). If statistically or clinically significant between-group differences are noted, we will conduct sensitivity analyses controlling for the unbalanced variables to assess the impact on the inference for the treatment groups. Prior to conducting all of the statistical analyses outlined below, we will evaluate the assumptions of the statistical models and outliers and influential cases will be screened for and removed. All tests will be two sided with type I error of 5%. In order to reduce type I errors, secondary outcomes will be examined using an alpha = .01.

Aim 1: Primary Hypothesis. Following 8 weeks of treatment, a greater improvement in LBP-related disability and physical function (as measured by change in Quebec LBP Disability score and self-selected gait speed, respectively) will be observed for individuals that receive HIP+ compared to spine-focused rehabilitation (SFR).

Quebec score and gait speed will be used to test our specific hypotheses about short-term (immediately post-treatment) and longer-term (6-months post-randomization) changes in disability and pain severity. We will use linear mixed models with time (baseline, 8 weeks and 6 months) and the group*time interaction as fixed effects while controlling for repeated measures using an unstructured correlation matrix between time points. The effect of time will be treated as categorical. No main effect for treatment is included as the baseline means are assumed and constrained to be equal due to randomization. We will also control for site and sex as fixed effects since these are stratification factors in the randomization. We will use linear contrasts to test HIP+ versus SFR at 8 weeks and 6 months (Aim 1). GLMM assumptions include homoscedasticity, normality, and linearity using standard graphical methods, the Shapiro-Wilk test, and Box-Cox test respectively. If model assumptions are violated, we will consider transformations (e.g. Box-Cox method) that can be applied but maintain interpretability. We will test the secondary outcome measures related to Aim 1 in the same fashion to identify which outcomes should be considered in future trials.

The rates of individual adverse events and serious adverse events that occur >10% and adverse events classified by organ system and relatedness will be calculated for each group and compared using Chi-square or Fisher's exact tests.

Aim 2: Hypothesis. Reductions in hip joint pain, increases in hip strength and increases in functional self-efficacy will be associated with improvements in LBP-related disability and physical function.

Two sets of regression analyses will be used to determine the degree to which changes in hip pain, hip strength and functional self-efficacy explain changes in LBP-related disability and physical

function, as measured by change in Quebec score and gait speed, respectively. The first set of models will examine the change from baseline to immediately post-treatment (8 weeks) and the second set from immediately post-treatment to 6 month follow up for Quebec scores. The second set will do the same but for changes in gait speed. Sequential Multiple Linear Regression Models will be used to test if predictors of interest are related to the outcomes after adjusting for potential covariates. This can be evaluated by testing the ΔR^2 that results from adding subsequent blocks of predictors to each model. If the block is significant, then the tests of the individual predictors will be examined. In the first block will be covariates that are potential confounders (i.e. age and sex) as well as the baseline values of hip pain, hip strength and self-efficacy. [Internal rotation strength relative to body mass, will be chosen as a representative hip strength measure, based on strength of association in our original data]. In the second block of each model will be the treatment group and change values for the predictors of hip pain, hip strength and self-efficacy. All assumptions for models will be tested: multicollinearity by examining the Variance Inflation Factor and Condition Index; normality using Shapiro-Wilk test; Homoscedasticity using the Breusch-Pagan test; and Linearity using the Box-Cox test. If assumptions are violated, transformations suggested by a Box-Cox test will be employed; if that fails Generalized Linear Models will be used.

Additionally, as an exploratory analysis a path analysis will be used to test if the relationship between baseline hip measures (pain, strength, and self-efficacy) and changes in disability and function are mediated by changes in the hip measures. Model fit will be examined using the chi-square model fit test, and standard fit indices (Root Mean Square Error of Approximation (RMSEA), Standardized Root Mean Residual (SRMR), Comparative Fit Index (CFI), and the Tucker-Lewis Index (TLI)) and to address the research question the significance of the indirect effect will be examined. It is likely that this analysis will be underpowered given the number of variables included. However, the analysis will provide a basis for further hypothesis generation and inform the follow-up study.

Reporting: Results will be disseminated through grant applications and written publications in reputable medical journals, as well as through professional presentations.

A description of this clinical trial will be available on <http://www.ClinicalTrials.gov>, as required by U.S. Law.

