1. Explore whether a hip-focused treatment leads to reduced disability and improved physical function when compared to a low back-focused treatment in an at-risk hip-spine subgroup (i.e. those with both hip pain and weakness, in addition to low back pain).
2. Determine what contributes to improvements in disability and physical function in this at-risk hip-spine subgroup.

6. PROCEDURES Describe all procedures involving human subjects for this protocol. Include copies of all surveys and research measures.

Study Participants.

Participants with moderately intense (LBP rated at least 4/10), chronic LBP (pain of at least 3 months) that impacts daily activities with concurrent hip pain and hip weakness will be recruited from newspaper and online advertisements, as well as from databases of former study participants who have agreed to be contacted for future studies. The sample will be recruited from one of three areas in this multi-site clinical trial: Newark, DE and surrounding communities, Pittsburgh, PA and surrounding communities and Durham, NC and surrounding communities.

Design and Randomization Plan.

In total, 180 participants meeting the inclusion/exclusion criteria will be randomly assigned into one of two intervention groups: (1) spine treatment supplemented with a hip-focused manual therapy and hip-focused exercise intervention, or (2) spine-focused rehabilitation with stationary cycling. We will use statistical software to generate a randomization plan that ensures by the end of the study that an equal number of participants are randomly assigned to each of the two treatment conditions. We will perform randomization separately in men and women given the reported sex differences in pain conditions among older adults²⁵, this approach will ensure equal randomization of men and women into both randomization groups. The treatment assignments will be uploaded into the web-based data entry application for the study. A participant's study allocation will be revealed to approved study personnel (i.e. not physical therapy testers) once all eligibility criteria have been entered and eligibility is confirmed.

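### The Aim 1 adjusted sensitivity analysis is run only if baseline differences appear, and chance differences choose its covariates; one fixed, always-run covariate set would be better, and the primary model is unaffected

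*Combined protocol and SAP*

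**What the plan says.** All of this is in the combined protocol and SAP, mostly in section 10, Statistical Analysis.

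- Purpose of the baseline comparison: "We will compare the two groups on baseline characteristics to assess the adequacy of the randomization".
- Variables: "Baseline characteristics include analgesic use, age, number of comorbidities, body mass index, gender, and race/ethnicity". The verb leaves the list open.
- Consequence: "If statistically or clinically significant between-group differences are noted, we will conduct sensitivity analyses controlling for the unbalanced variables". The stated aim is to see how far the treatment inference is affected. No threshold is given for a clinically important difference, and no covariate set is named in advance.
- Significance level: "All tests will be two sided with type I error of 5" per cent. Only secondary outcomes get another level ("secondary outcomes will be examined using an alpha = .01"), so by its wording the baseline tests run at 5%.
- Primary Aim 1 model: categorical time and group-by-time with an unstructured covariance matrix, plus two covariates: "We will also control for site and sex as fixed effects since these are stratification factors in the randomization". Baseline outcome is handled as a response: "No main effect for treatment is included as the baseline means are assumed and constrained to be equal due to randomization".
- Size: "In total, 180 participants meeting the inclusion/exclusion criteria will be randomly assigned into one of two intervention groups", with equal numbers per arm and separate randomisation of men and women (section 6, Design and Randomization Plan).

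Aim 2, by contrast, names its covariates beforehand.

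**The concern.** A significance test of a baseline difference asks whether chance could have produced it. After proper random allocation the answer is already known to be yes, so the p-value says nothing about whether the randomisation was adequate. The plan itself relies on this elsewhere: the Aim 1 model constrains baseline means to be equal because of randomisation.

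The larger practical issue is what the comparison then controls. It decides whether an adjusted analysis is run and which variables go into it. A chance difference in a variable unrelated to outcome triggers adjustment. A variable that predicts outcome but happens to be balanced does not. The alternative clinical trigger does not repair this, because it has no threshold and so becomes a judgement made on data split by arm.

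At stake is the value of the robustness check. If its existence and content follow from the observed data, a reader cannot compare it with a plan. It also makes little use of baseline data that the trial collects anyway.

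**Working it through.** The plan gives no figure on this point to reproduce.

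**1. How often the statistical trigger fires when randomisation is sound**

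Inputs: six listed characteristics, 5% level (section 10). Sex is a randomisation stratum and already in the model, so five is the more relevant count. Independence of the variables is assumed.

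- Six variables: 1 − 0.95^6 = 0.265
- Five variables: 1 − 0.95^5 = 0.226

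The clinical trigger would add to this by an unknown amount.

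**2. Whether selection follows prognostic strength**

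Simulation under no treatment effect: 20,000 trials per setting, 90 per arm (180 / 2), five independent covariates of which one has correlation r with outcome, simple analysis of covariance, statistical trigger only. The values of r are assumptions.

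| r | Prognostic covariate selected | Type I error, adjust only if significant | Unadjusted rejection rate when that covariate is significantly unbalanced |
|---|---|---|---|
| 0 | 4.9% | 0.049 | 5.8% |
| 0.3 | 5.1% | 0.048 | 9.9% |
| 0.5 | 4.9% | 0.044 | 19.2% |

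A covariate is picked about 5% of the time whatever its link with outcome. Even if the conditionally adjusted result were taken as the trial's result, type I error would not exceed 5%. Always adjusting for the prognostic covariate gave 0.049 to 0.051.

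**3. What an imbalance at the cut-off would do**

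The 5% cut-off is a standardised difference of 1.96 × √(2/90) = 0.292. The shift in the unadjusted effect is r × 0.292 SD, or r × 1.96 standard errors:

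- r = 0.3: 0.088 SD, 0.59 standard errors
- r = 0.5: 0.146 SD, 0.98 standard errors
- r = 0: none, although the rule would still adjust

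**4. Precision available from a fixed set**

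Standard-error ratio = √(1 − R²), where R² is the share of residual outcome variance explained. The plan gives no R²; 5% to 10% is an assumption.

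- R² = 0.05: √0.95 = 0.975, a fall of about 2.5%
- R² = 0.10: √0.90 = 0.949, a fall of about 5%

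**5. Why covariate-by-time terms are needed**

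Baseline is a response in the Aim 1 model, so a covariate main effect forces one slope on all time points. As an illustration, take baseline and one follow-up, residual variances of 1, within-person correlation 0.6, a standardised covariate with slope 0 at baseline and 0.3 at follow-up (all assumed). The precision of the follow-up contrast depends on the variance of follow-up given baseline:

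- No covariate: 1 + 0.3² − 0.6² = 0.73
- Main effect only (common slope 0.15): 1.0225 − 0.5775² / 1.0225 = 0.696; √(0.696 / 0.73) = 0.977, a fall of about 2%
- With covariate-by-time: 1 − 0.6² = 0.64; √(0.64 / 0.73) = 0.936, a fall of about 6%

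**The case against.** The best defence is that only a sensitivity analysis is involved. The Aim 1 model is the same whatever the baseline comparison shows. It always includes site and sex and always accounts for the baseline value of each primary outcome. The sensitivity analysis is meant as a robustness check, not a precision gain, and its trigger, purpose and main candidates are written down. The 26% is the chance of running one extra model, not a measure of harm. A trigger on sex would change nothing, since sex is already in the model. An open list also lets the team respond to an imbalance nobody foresaw. All of this stands.

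It rules out several stronger readings that a reader might infer:

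- **That the primary inference is compromised or type I error inflated.** The primary model is pre-specified, and the simulation shows no inflation.
- **That strong predictors are left out altogether.** The omission concerns age, body mass index, comorbidities, analgesic use and race/ethnicity in Aim 1. Nothing in the documents shows that any of these is a strong predictor once baseline outcome, site and sex are in the model. Aim 2 adjusts for age in any case.
- **That the judgement is made after unblinding.** The documents do not say when, by whom or with what knowledge of arm identity the comparison is made.

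The defence does not justify the trigger itself. Step 3 shows that an imbalance matters in proportion to how well the variable predicts outcome, which a baseline p-value does not measure. A fixed adjusted model also answers the robustness question, and does so in every realisation of the trial.

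**Conclusion.** The point holds, limited to the Aim 1 sensitivity analysis. Baseline tests cannot validate the randomisation. As written, chance differences, or an undefined clinical judgement, decide whether adjusted results exist and for which variables. On the statistical route alone that would happen in about 23% to 26% of sound trials, assuming independent variables and the 5% level. The other five listed characteristics enter an Aim 1 model only if found unbalanced.

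The consequence is a data-dependent robustness check and some unused precision in it: about 2.5% to 5% of its standard error if the covariates explain 5% to 10% of residual variance, an assumption the documents can neither confirm nor refute. The primary estimate and its error rate do not change. This is a worthwhile tidying of the plan, not a threat to its conclusions.

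**What to change.** In section 10, Statistical Analysis:

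1. Delete the testing trigger and the statement that the comparison judges the randomisation. Describe baseline characteristics by arm without p-values.
2. Pre-specify one supporting adjusted analysis of Quebec score and gait speed, run whatever the balance. Add analgesic use, age, number of comorbidities, body mass index and race/ethnicity to the Aim 1 model, each with its covariate-by-time term. Site and sex are already there. State the coding of each covariate beforehand.
3. Label any further model prompted by a notable imbalance in an unlisted variable as post hoc. This keeps the flexibility the current rule offers.

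The cost is a few lines of text and one extra model per primary outcome, using baseline data already collected. That model gives up some degrees of freedom: with three time points, each single-term covariate uses three parameters, so five use 5 × 3 = 15, and more if race/ethnicity has several levels. The primary analysis and the sample size stay as they are.

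### Outliers and influential cases are to be removed before every analysis, with no stated rule and no all-data result, so neither intention-to-treat nor the 5% error rate is assured

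*Combined protocol and SAP*

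**What the plan says.** All of this stands in the combined protocol and SAP, Section 10 (DATA), under Statistical Analysis.

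- Analysis principle: "The primary analyses will be done using intention-to-treat methods".
- Removal: "Prior to conducting all of the statistical analyses outlined below", the plan continues, "we will evaluate the assumptions of the statistical models and outliers and influential cases will be screened for and removed". The scope therefore covers the Aim 1 primary and secondary models, the Aim 2 regressions and the exploratory path analysis.
- Error rate: "All tests will be two sided with type I error of 5" (per cent). Secondary outcomes are tested at 0.01.
- Violated assumptions, Aim 1: "If model assumptions are violated, we will consider transformations (e.g. Box-Cox method) that can be applied but maintain interpretability".
- Violated assumptions, Aim 2: "If assumptions are violated, transformations suggested by a Box-Cox test will be employed; if that fails Generalized Linear Models will be used".

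The only sensitivity analysis described is adjustment for baseline variables found to differ between the arms. Nowhere do the documents define an outlier or influential case, name a statistic or threshold, say whether one observation or a whole participant goes, say whether the screener knows the treatment group, or plan a result with the removed cases put back.

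**The concern.** The instruction is to remove, not to flag, query or correct. An influential case is often a perfectly valid measurement, so the clause goes beyond cleaning. Deleting valid post-randomisation outcomes because of their values means that the arms compared are no longer the arms randomised. The conflict with intention-to-treat is plainest if whole participants are dropped. It is weaker if single observations are dropped, because the participant's other visits stay in the mixed model.

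Two things are at stake. The first is the error rate: when extremes are judged against a model that contains the treatment effect and the model is then refitted, the residual variance is understated and the test can reject too often. The second is the estimate: if benefit is concentrated in some participants, those participants look like outliers and their removal erases part of the effect. With no all-data result planned, a reader of the trial report could not tell whether either had happened.

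**Working it through.** **Inputs from the documents.** 180 participants, equal allocation, so 90 per arm (Section 6, Design and Randomization Plan). Linear mixed model with three categorical visits, group-by-time terms, no treatment main effect, unstructured correlation, and site and sex as fixed effects. Contrast at 8 weeks; two-sided 5% (Section 10).

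**Assumed inputs.** The documents give no SDs, correlations or dropout. The simulations assume normal errors, complete data, a correlation of 0.6 between baseline and each follow-up, and 0.7 between the two follow-ups.

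**Method.** Simulate trials, fit the model, flag cases, remove them once, refit, and count how often p < 0.05. Residual rules flag |residual / its SD| > c, with residuals from the fitted model. Pooled rules flag values more than c SDs from the overall mean, ignoring arm. Simulation standard error is √[p(1−p)/R]. At p = 0.05 it is 0.34 points for R = 4,000 and 0.28 for R = 6,000, the two null runs used.

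**Step 1: the plan's own figure.** With all data kept, type I error is 4.80% (4,000 trials) and 5.08% (6,000 trials). The stated 5% is reproduced.

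**Step 2: type I error after one pass of removal, planned mixed model.**

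| Rule | Type I error |
|---|---|
| Cook's distance > 1 | 5.1% |
| Pooled 3 SD or 2 SD | 4.9-5.4% |
| Absolute residual > 3 | 5.3-5.7% |
| Cook's distance > 4/n | 6.2% |
| Absolute residual > 2 | 8.4-10.6% |

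The ranges reflect the type of residual or value screened and the unit removed. At a residual cut-off of 2 with whole-participant removal, 19.0 of 180 participants (19.0/180 = 10.6%) are lost, although the simulated data contain no true outliers.

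**Step 3: cross-check.** A simpler baseline-adjusted comparison at one follow-up (20,000 trials) gives 5.0% with all data, 5.9% at > 3, 7.5% at > 2.5, 11.1% at > 2 and 10.4% for Cook's distance > 4/n. The last is higher than in the planned model, so the 6.2% is the figure to use. With t5, t3 or lognormal errors, the removal rules tried give 6.1-9.6%. A fixed rule using residuals from a model without group gives 4.9-5.0%.

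**Step 4: the estimate.**

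- Uniform benefit of 0.30 SD: residual rules leave 0.30. A pooled 3 SD rule gives 0.29-0.30. A pooled 2 SD rule gives 0.25-0.26, with power falling from 70% to 56-60%.
- Concentrated benefit, assumed: 15% of HIP+ participants gain 2.5 SD, so the mean difference is 0.15 × 2.5 = 0.375 SD. Simulated with all data it is 0.37. It falls to 0.32-0.35 at a residual cut-off of 3 and to 0.16-0.28 at 2.

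**Step 5: who is removed.** Under that concentrated benefit, with approximate marginal residuals over the three visits and a cut-off of 2, whole-participant removal takes 13.2 from HIP+ and 6.0 from the comparator (14.7% and 6.7% of 90). Removal of single 8-week observations takes 7.3 and 1.6.

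**The case against.** The strongest defence is that most sensible rules do little harm. Cook's distance > 1, a residual cut-off of 3 and pooled cut-offs all stay between 4.9% and 5.7%, and a group-blind rule holds 5%. The 8-11% needs a cut-off of 2, which trims heavily. The concentrated-benefit case is an illustration that nothing in the documents establishes. The trial is also partly framed as asking whether the approach merits further study, and the clause may have been aimed at recording errors.

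Much of this stands, and it limits the claim to an error rate that is not assured. It does not rescue the clause. The text does not confine removal to errors, it does not choose any of the harmless rules, and the choice cannot be audited afterwards. Nor is blinding enough on its own. In a single-follow-up check, a group-blind cut-off of 2 kept error at 5.1% but cut the concentrated benefit from 0.37 to 0.11 SD.

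Four stronger readings are tempting and are not supported:

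- A reader might infer that the trial's type I error is inflated. That depends on a rule the plan does not give.
- A reader might infer repeated screening, or a rule picked after seeing results, either of which would raise error much further. The plan puts screening before the analyses and mentions no repetition, so these are misuse scenarios.
- A reader might infer that removal breaks the model's baseline assumption ("No main effect for treatment is included as the baseline means are assumed and constrained to be equal due to randomization"). In simulation the baseline gap between retained arms was 0.03 SD under a pooled 2 SD rule on change scores and nil under residual rules, which is negligible.
- A reader might infer that removals would fall about eight to one on HIP+. That ratio arises only in a single-follow-up analysis. Over the planned three visits it is roughly two to one for whole participants.

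**Conclusion.** The clause is wrong as written; this is more than a missing detail. Followed literally, "outliers and influential cases will be screened for and removed" permits valid randomised outcomes to be deleted from the primary models, against the intention-to-treat statement in the same paragraph, and no planned result would show the effect.

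The size depends on the unstated rule: about 5-6% type I error under lenient, pooled or Cook's distance rules, about 8-11% at a residual cut-off of 2, and a concentrated benefit reduced by anything from slightly to more than half. These figures rest on 90 per arm, complete data, mainly normal errors and assumed correlations. They show direction and range and do not predict this trial's error rate. The conflict with intention-to-treat rests on the text alone and needs none of these assumptions. Because the clause acts on the primary analysis and costs little to change, it should be corrected before any outcome data are analysed.

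**What to change.** Replace the removal clause in Section 10 with wording such as:

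> Outliers and influential cases will be checked, blind to treatment group, for data-entry or measurement error and corrected where source data show an error. All valid observations from all randomised participants are retained in all analyses (Aim 1 primary and secondary outcomes, the Aim 2 regressions and the path analysis). For the Aim 1 models, the effect of influential cases is examined in a labelled sensitivity analysis using one pre-specified rule (for example, one pass removing single observations with an absolute studentised marginal residual above 3), reported beside the all-data result.

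The cut-off of 3 is an example. What matters is that one rule, including the type of residual and the unit removed, is fixed in advance. The steps for violated assumptions under Aim 1 and Aim 2 can stay as they are.

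The cost is a few sentences, one extra model run per Aim 1 outcome, and no new data. The downside is that genuine extreme values stay in and may widen the confidence interval somewhat; that widening was not computed.
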